## **4.5. Administration of Hydroxychloroquine**

The hydroxychloroquine used in these human trials is a 4-aminoquinoline compound (hydroxychloroquine sulfate) supplied as a 200mg tablet for oral administration. As described below, these tablets will be prepared in 100mg increments and over encapsulated for this trial.

Hydroxychloroquine must be stored below 25°C/77°F.

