### **7.3. Protecting Against or Minimizing Potential Treatment Risks**

Participants who have other active serious medical problems will not be enrolled. Frequent monitoring of participants with history, physical examination, and laboratory studies will allow for early identification of adverse events. Every attempt will be made to minimize the number of venipunctures. Participants will be screened for G6PD deficiency and excluded if present.

To mitigate potential ophthalmologic risk, a fundus photograph or examination will be attempted at Baseline, and OCT and visual field examinations will be attempted annually in all participants. Participants with a successful OCT examination may continue with the study per protocol. If neither the OCT nor visual field examination can be successfully completed (e.g., in very young children), these

examinations will be re-attempted on an annual basis while the participant continues on study drug. The target dose of hydroxychloroquine will be 5.0 mg/kg/day to a maximum of 400mg. This is below the dose associated with ophthalmologic risk. Moreover, individuals who reach study endpoint (abnormal glucose tolerance) will be considered to be a non-responder and withdrawn from therapy, thus decreasing duration of exposure.

Individuals will be informed of potential impact on skin, sleep, gastrointestinal symptoms, and muscle aches. If symptoms continue or are intolerable, drug dose may be temporarily reduced or stopped, at the discretion of the investigator in consultation with the medical monitor. If signs or symptoms are consistent with infectious mononucleosis, evaluation may include measurements of EBV serology and viral load as clinically indicated.

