The Adverse Events summary tables will include number of adverse events, the number of subjects in each treatment group in whom the event occurred, and the incidence of occurrence and should be grouped by system organ class, preferred terms and/or other interested variables (e.g., relatedness, intensity and seriousness). [TABLE]

When calculating the incidence of adverse events, or any sub-classification thereof by treatment, time period, severity, etc., each subject will only be counted once and any repetitions of adverse events will be ignored; the denominator will be the total population size. Deaths, Serious Adverse Events and other Significant Adverse Events

All formal testing of adverse effects will be based on the subject as the experimental unit. Thus, for comparing incidence of AE within system organ by treatment group, a one-sided Fisher's exact test will be conducted at 0.05 level (higher incidence in experimentally treated group is the alternative hypothesis). Also, highest AE grade will be determined for each subject and compared by treatment group using a 2 sample Wilcoxon test (one-sided at 0.05). No correction for multiple testing will be employed in order that the statistical power is maintained.

9. Reporting Conventions

P-values ≥ 0.01 will be reported to 2 decimal places; p-values less than 0.01 and >0.001 will be reported to 3 decimal places; p-values less than 0.001 will be reported as " <0.001 ". The mean, standard deviation, and any other statistics other than quantiles, will be reported to one decimal place greater than the original data. Quantiles, such as median, or minimum and maximum will use the same number of decimal places as the original data. Estimated parameters, not on the same scale as raw observations (e.g. regression coefficients) will be reported to 3 significant figures.

10. Per Protocol Analysis

Quantifying the evidence of any dose response relationship is part of a complete analysis of any well-run and completed clinical trial. This is especially true when the trial is negative when testing the primary outcome. To explore whether there is evidence that protocol treatment deviations may have played a role in the negative outcome, we plan to assess the treatment hazard ratio by the degree of compliance (percent missed infusions) to the protocol scheduled dose in a quantitative manner.

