Using the Cox model we will assess the evidence for an effect of treatment compliance including the entire cohort. The number of infusions of treatment and the treatment dose (in a separate model) will be introduced into the model as a continuous variable (0=received no therapy; 1 = received the full prescribed dose) along with the interaction term with treatment group to determine its effect on risk. The significance level of the interaction term (compliance value if hydroxychloroquine subject; 0 otherwise) will be considered important if it is approximately 0.05 or less one-sided and the coefficient is negative (indicating lower risk with greater compliance). The procedure for including covariates, such as age, will follow the set up procedure as described above under Primary and Secondary analyses.

11. Technical Details

The analysis will be performed in R, S-Plus or SAS. The distributional assumptions as well as other assumptions underpinning the planned analyses will be checked.

12. References

1. Cox DR: Regression model and Life Tables *J R Stat Soc* 34B:187-220, 1972
3. DeMets DL, Lan G: The alpha spending function approach to interim data analyses. *Cancer Treat Res* 75:1-27, 1995
4. JM Lachin. Futility interim monitoring with control of type I and II error probabilities using the interim Z-value or confidence limit. *Clinical Trials* 2009; 6 (6) 565-573
6. Ursini et al. (2015) *Medicine* 94 DOI: 10.1097/MD.0000000000000888
7. Matsuda and DeFronzo *Diabetes Care* 22:1462–1470, 1999

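### SAP section 10 measures compliance with an oral capsule in infusions, and leaves the period and timing of its alternative dose measure undefined, so the result depends on an unstated choice

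*SAP*

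**What the plan says.** SAP section 10 (Per Protocol Analysis) explores whether departures from treatment could explain a negative result: "we plan to assess the treatment hazard ratio by the degree of compliance (percent missed infusions) to the protocol scheduled dose". Everyone is included: "Using the Cox model we will assess the evidence for an effect of treatment compliance including the entire cohort". Two exposure measures are named, each in its own model: "The number of infusions of treatment and the treatment dose (in a separate model) will be introduced into the model as a continuous variable". The scale is given as "0=received no therapy; 1 = received the full prescribed dose) along with the interaction term with treatment group to determine its effect on risk". One term carries the decision: "The significance level of the interaction term (compliance value if hydroxychloroquine subject; 0 otherwise"; it "will be considered important if it is approximately 0.05 or less one-sided and the coefficient is negative".

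The section does not say over what period the full prescribed dose is counted, whether the value is fixed or updated, how it is derived from returned medication, or whether a treatment main effect is in the model. SAP section 4.2, by contrast, names time-dependent covariates for longitudinal factors.

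In Protocol section 4.5 the drug is "supplied as a 200mg tablet for oral administration", over-encapsulated for the trial, and section 4.5.1 sets a daily dose. Appendix 2 schedules medication accountability at month 3, month 6 and six-monthly after that. Under Protocol section 7.3 a participant who reaches abnormal glucose tolerance "will be considered to be a non-responder and withdrawn from therapy, thus decreasing duration of exposure". Sections 3.9.2 and 8.1 also describe follow-up after Stage 2 as being without study therapy.

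**The concern.** There are two separate problems.

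- **The named variable does not exist.** No infusion is given in this trial, so a count or percentage of infusions cannot be computed.
- **Changing the word does not complete the definition.** A single 0-to-1 value per participant must be totalled over some period. Dosing ends at the endpoint, and longer event-free follow-up leaves more time to stop the drug. The total is therefore partly a consequence of the event time that the Cox model is meant to explain.

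The analysis matters most after a negative primary result, when readers will ask whether poor adherence hid a benefit. If the denominator is chosen at analysis, that choice can set the sign of the apparent compliance effect, and under one choice a real on-drug effect would almost never be found.

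**Working it through.** **1. The plan's own figure.** Section 10 states no power of its own, so the trial's power fixes the scale. With 80 events, 2:1 allocation and hazard ratio 0.50: sqrt(80 x 2/3 x 1/3) x ln 2 = 4.216 x 0.693 = 2.92; 2.92 - 1.96 = 0.96; power = 83.2%. The stated 83% is reproduced. The placebo hazard is -ln(0.60)/2 = 0.2554 per year, and the two-year rate on active drug is 1 - 0.60^0.5 = 22.5%, as stated.

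**2. Why one value per person depends on event time.** Illustration only: take a participant who would stop the drug at 1.5 years and has 4 years of planned follow-up.
- Doses counted to the event: an event at 1 year gives 1/1 = 1.00; an event at 3 years gives 1.5/3 = 0.50. Early events look more compliant.
- Doses counted over planned follow-up: the same events give 1/4 = 0.25 and 1.5/4 = 0.375. Someone who never stops scores 0.25 with an event at 1 year and 1.00 if event-free. Early events look less compliant.

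**3. Simulation with no drug effect and no compliance effect.** Inputs from the documents: 135 and 66 participants, 40% two-year placebo rate, 10% two-year dropout, 4 years' accrual, end at year 6, exponential times. Inputs assumed: individual adherence Beta(17,3), and random drug stopping at the annual rates shown. The Cox model holds treatment, compliance and their interaction; 500 trials per row.

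| Compliance value | Stopping per year, active/placebo | Compliance term, median log HR | Interaction, median | SAP rule met | Interaction significantly positive |
|---|---|---|---|---|---|
| To the event | 15%/15% | +1.38 (significantly positive in 60%) | -0.03 | 5.6% | 4.2% |
| To the event | 25%/10% | +1.28 (42%) | +0.25 | 1.8% | 7.6% |
| Planned follow-up | 15%/15% | -3.37 (significantly negative in 100%) | -0.03 | 6.0% | 7.0% |
| Planned follow-up | 25%/10% | -3.78 (100%) | +0.88 | 0.6% | 25.8% |
| Constant over time | 15%/15% | +0.17 (no excess either way) | -0.26 | 5.6% | 4.8% |

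The Monte Carlo standard error is sqrt(0.05 x 0.95/500) = 1.0 point near 5%.

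Further runs of 300 to 400 trials agree. At 10% stopping in both arms the compliance term was +1.19 to +1.40 (to the event) and -3.17 to -3.33 (planned). At 25% against 10% the planned-denominator interaction was +0.72 to +0.73, significantly positive in 24 to 27%.

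Within the active arm alone, at 15% stopping, the compliance coefficient was +1.32 (significantly positive in 87%) to the event and -3.41 (significantly negative in 100%) over planned follow-up. A within-arm dose-response reading is therefore biased too.

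**4. The same null with a time-updated value.** With cumulative compliance updated to each event time, the interaction median was -0.07 to +0.07 and the rule was met in 2.0 to 5.8% of trials.

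**5. A true effect that acts only while on drug** (hazard halved on drug; stopping 15% vs 10% or 25% vs 15% per year in the two arms). Share of trials in which the interaction rule is met, over several sets of 300 to 400 runs:

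| Covariate | Rule met |
|---|---|
| Fixed, to the event | 14 to 24% |
| Fixed, planned follow-up | 3 to 8% |
| Time-updated, cumulative | 20 to 32% |
| Time-updated, current on-drug status | 29 to 44% |

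Compared within the same runs, the gain over the fixed to-event value is about 3 to 12 points for cumulative compliance and about 15 to 20 for current status. Current status is favoured by construction, because it is the mechanism that generated the data.

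**6. If treatment is left out of the model,** which the text does not exclude, the interaction absorbs the treatment effect. At a true hazard ratio of 0.50 with no compliance effect, the rule was met in 65 to 93% of trials.

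**The case against.** A reader might infer that the analysis cannot be run at all and would falsely declare compliance important. The documents do not support that, for several reasons.

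- The dose model is separate from the infusion model. It could be run once its period is defined, since accountability data are scheduled.
- The SAP never says the value is fixed or taken at the end of follow-up. That is an inference from the 0-to-1 wording and from the contrast with section 4.2. The certain defect is that denominator and timing are unstated.
- The rule applies only to the interaction and requires a negative sign. The large null artefacts are in the compliance main effect, which is not tested. With equal stopping the interaction is centred near zero. At 10% stopping the rule was met in 2.3 to 2.8% (to the event) and 8.7 to 10.7% (planned). In the run giving 10.7%, the positive direction also showed 10.7%: some excess, but no directional bias.
- Counting doses over planned follow-up is the less natural reading of compliance with a scheduled dose, because nothing is scheduled after Stage 2.
- The discontinuation rates are assumed. Protocol section 2.2.3 expects few to stop for side effects, and adherence that is constant over time gives no artefact.
- Low power mostly reflects 80 events and few stoppers, and a better covariate shares that limit.

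All of these stand, and they narrow the point. They do not remove it: the infusion variable has no data, the period is open, the main effect and any within-arm reading are biased, and unequal stopping harms the tested term. Unequal stopping is plausible, because Protocol section 4.5.1 withholds study drug for adverse effects.

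**Conclusion.** The point holds in a limited form and should be corrected. That the infusion model cannot be computed follows from the text alone. The rest depends on reading compliance as one whole-follow-up value and on assumed random discontinuation of 10 to 25% per year.

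On those terms, the sign of the compliance coefficient follows the denominator: about +1.3 to the event and about -3.2 over planned follow-up, with no true effect. The tested interaction is largely protected when the arms stop equally. With 25% against 10% stopping and the planned denominator it moves against benefit, by about +0.7 to +0.9, and is significantly positive in about 25% of null trials. The same denominator finds a real on-drug effect in about 3 to 8% of trials, so a null result there would say little about adherence.

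A general false-positive problem is not shown for the tested interaction when treatment is in the model. The analysis is exploratory and does not touch the primary test.

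**What to change.** Reconcile SAP section 10 with Protocol section 4.5 and, before unblinding:

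- Replace infusions with doses taken divided by doses prescribed, from the study-medication accountability data. Count only doses scheduled while the participant is at risk and before the endpoint.
- Enter the ratio as a time-dependent covariate updated at each visit. Choose in advance between cumulative compliance and current on-drug status (or recent-interval compliance). The latter has more power if the effect acts only while on drug.
- State that treatment, compliance and their interaction are all in the model.
- Label the analysis exploratory, since compliance is not randomised even when correctly timed.

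The cost is SAP wording and modest extra programming, with no new data. The expected gain is mainly a defined, unbiased term; the gain in power over a fixed to-event value is modest.
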